## 2 Project summary

Peripheral arterial occlusive disease (PAD) is one of the most common diseases of the elderly with an overall prevalence of about 3-10% [1]. As life expectancy increases, new treatment concepts and new diagnostic procedures are needed. In addition to the possibility of endovascular treatment and open surgery, in some cases there is also the possibility of a conservative therapeutic approach, e.g. with medication [2].

To date, the only independent non-invasive validation of these treatment options is the measurement of macrocirculation in the form of Color-Coded Vascular Duplex Sonography (CCDS), the Ankle Brachial Index (ABI) or the measurement of walking distance. The S3 guideline for diagnosis, therapy and medical aftercare of PAD published 2015 by the DGA (Deutsche Gesellschaft für Angiologie und Gefäßmedizin [German Society for Angiology and Vascular Medicine]) recommends aftercare in the sense of clinical examinations, especially for patients after vascular surgery. For the validation measures already mentioned, however, there are not infrequent patient groups for which these methods provide only insufficient or unusable results (e. g. diabetes mellitus, terminal renal failure). In these cases, independent verification of the therapeutic success would have to be performed using angiography (digital subtraction angiography, CT angiography or MR angiography). However, this is not routinely performed in the respective patient populations due to the associated risks (including radiation exposure, contrast agent administration, invasiveness).

Multispectral Optoacoustic Tomography (MSOT) now provides a new non-invasive diagnostic tool that may be able to fill this diagnostic gap.

The aim of this cross-sectional study is to define an independent parameter using the MSOT method, which allows a statement about the current perfusion situation of the lower extremity and correlates with the angiography, which is considered the gold standard. For this purpose, patients of different PAD stages, who already underwent routinely angiographies in advance, will be included. In addition, a control group of healthy volunteers (prior angiography not obligatory) will be examined.

### **3.4 Sponsoring**

Department of Vascular Surgery; internal financing and by grants from the ELAN Foundation.

## 4 Scientific background

[figure not shown]
Since 2017, the University Hospital Erlangen (Department of Medicine 1, Department of Pediatrics and Adolescent Medicine) has a Multispectral Optoacoustic Tomograph (MSOT) at its disposal, which is funded by the DFG (Deutsche Forschungsgemeinschaft [German Research Foundation]). This allows, comparable to sonography, a non-invasive, quantitative imaging of the composition and oxygenation of target tissues such as the muscles.

In the MSOT, similar to conventional sonography, a transducer is placed on the skin and instead of sound, energy is applied to the tissue by means of light flashes. This leads to a constant change of minimal expansion and contraction (thermoelastic expansion) of individual tissue components or molecules. The same examination unit can then detect the resulting sound waves. Previous studies have shown that the quantitative determination of hemoglobin can provide information on blood flow and inflammatory activity in the intestine of patients with Crohn's disease [3, 4]. In the newly configured device (Acuity Echo, iThera Medical GmbH, Munich, custom-made), an extended spectrum of laser light can be used, which ultimately enables not only the detection of hemoglobin and its oxygenation levels, but also the detection of other markers such as collagen and lipid. Figure 1 shows an example of the feasibility of these images using MSOT.

These parameters have already been successfully measured, validated and reproduced in preliminary studies.

Of special interest is the muscle perfusion in PAD patients, in whom due to previous diseases such as severe chronic renal insufficiency or diabetes mellitus the ABI measurements or the implementation of a CCDS due to a progressive stiffening of the vessel wall (Mönckeberg-Mediasclerosis) do not provide sufficiently valid values. Furthermore, there are also groups of patients who are unable to complete a treadmill examination to determine the possible walking distance due to previous illnesses or operations. To date, there are no non-invasive measurement methods besides the MSOT, which are able to make statements in a transcutaneous manner about muscle perfusion for these patient groups. Here, the non-invasive MSOT method could maintain its value in the diagnostics of PAD patients and close the diagnostic gap.

In this cross-sectional study, the MSOT method for monitoring muscle perfusion in a large group of PAD patients will be investigated for the first time to define threshold values. Patients of different stages of PAD will be examined in this study in case of previously performed angiography, which is the diagnostic gold standard and will serve as a reference. In addition, a healthy control group is included as a comparison group, but prior angiography is not mandatory in this group. A validation of the results will be performed on a group of patients to be examined and analyzed at a later time point.

**Figure 1: Visualization of the optoacoustic signal in a self-experiment**

From left to right: B-scan ultrasound (b/w, RUCT), collagen signal (red, collagen), lipid signal (green, lipid), oxygenated/deoxygenated hemoglobin signal (blue-purple, Hb/HbO2), optoacoustic overlay (OA-merge). From top to bottom: Achilles tendon (longitudinal section), Achilles tendon (cross section), palmaris longus tendon, glisson capsule of liver. Note the clear signal of the connective tissue structures (tendon, capsule) in the collagen signal (red), and the surrounding fatty tissue in the lipid signal (green).

(not published original data [name]&[name] 2017)

## 5 Study objectives

The aim of this study is to define an independent parameter for the diagnostic assessment of the perfusion situation of the calf muscle based on Multispectral Optoacoustic Tomography (MSOT) in a cross-sectional collective of healthy volunteers and patients with PAD in stages II-IV (study group 1). The gold standard is a previously performed angiography of the pelvic and femoral vessels based on routine diagnostics, this imaging is not mandatory for the healthy control collective. An independent validation group (study group 2) will validate the results found in study group 1.

### 5.1 Primary/secondary objectives and hypotheses

#### *Primary hypothesis:*

- Hemoglobin parameters in muscles of patients with PAD determined by MSOT (before and after active exercise) are suitable to predict relevant vascular stenosis and occlusion

#### *Secondary hypotheses:*

- The MSOT parameters for hemoglobin correlate with the perfusion parameters of the CCDS
- The MSOT parameters for hemoglobin correlate with the ABI
- The MSOT parameters for hemoglobin correlate with the walking distance
- The MSOT parameters for hemoglobin correlate with the clinical stage of PAD according to Fontaine and Rutherford

#### *Primary objectives:*

- Study group 1: Derivation of optimal diagnostic MSOT thresholds for hemoglobin through correlation with TASC classification for angiographic imaging (and CCDS if necessary) as references for relevant stenosis/occlusion in patients with PAD.

---

 Angiographic images are reviewed by two independent and experienced individuals to determine the type of TASC.

In the TASC classification for angiographic imaging, the pelvic and femoral arteries are assessed separately based on the extent and localization of the present stenoses/occlusions. However, the perfusion situation in the target region (calf muscle), that is measured by MSOT, results from a combination of both findings. In order to represent the circulation situation in the target muscle properly and to enable a correlation with the MSOT parameters measured there, it is necessary to regard the existing aorto-iliac and femoro-popliteal constellations of findings. For this purpose, 3 categories are established (1 – 3), that result from the occurring combinations of findings of both TASC classifications. The description of the categories can be found in the Statistical Analysis Plan (version 1.1, 01/20/2022).

- Study group 2: Validation of the diagnostic accuracy of MSOT, employing the cut-off values derived in study group 1, in terms of MSOT hemoglobin values through correlation with TASC classification for angiographic imaging as a reference of relevant stenosis/occlusion in patients with PAD in an independent cohort.

***Secondary objectives:***

- Determination of the quantitative fraction of oxygenated/deoxygenated/total hemoglobin and the MSOT-values at a wavelength of 800 nm in the area of the M. triceps surae before and after gait exposure determined by MSOT
- Correlation of the quantitative fraction of oxygenated/deoxygenated/total hemoglobin and the MSOT-values at a wavelength of 800 nm in the area of the M. triceps surae with the TASC classification in angiography
- Comparison of the difference between oxygenated and deoxygenated hemoglobin in the area of the M. triceps surae before and after gait exposure determined by MSOT
- Correlation of the difference between oxygenated and deoxygenated hemoglobin in the area of the M. triceps surae before and after gait exposure determined by MSOT with the TASC classification in angiography
- Determination of the quantitative lipid/ collagen signal fraction and the MSOT values at a wavelength of 930 and 1064 nm determined by MSOT
- Correlation of the flow profile and PSV of the CFA and A. poplitea determined by CCDS with the acquired MSOT parameters
- Correlation of the ABI with the acquired MSOT parameters
- Correlation of the walking distance with the acquired MSOT parameters
- Correlation of the clinical severity of PAD according to Fontaine and Rutherford classifications with the acquired MSOT parameters

## 5.2 Study type

Monocentric diagnostic cross-sectional study.

## 6 Target parameters

All measurements with MSOT are performed before and after muscle exposure in the area of the M. triceps surae. Eight MSOT wavelengths (715, 730, 760, 800, 850, 930, 1000 and 1064 nm) will be measured. For the investigation five calculated parameters

extracted from the measured wavelengths will also be taken into account (hb, hbO2, hbtot, collagen, lipid).

## 6.1 Primary target:

- Quantitative signal of hemoglobin (in arbitrary units)
  - *This target is measured non-invasively by MSOT*

## 6.2 Secondary targets:

- Oxygenation of the muscle, determination of oxygenated, deoxygenated hemoglobin, determination of lipid signal, determination of collagen signal
  - *These targets are measured non-invasively by MSOT*
- Flow profile of the A. femoralis communis and A. poplitea determined by CCDS
- ABI
- Actual walking distance standardized by treadmill examination
- Stage of PAD according to Fontaine and Rutherford
- Age, sex, risk factors for PAD
  - *These target values are either available in the electronic patient file or they are collected at presentation for the study.*
- Relevant underlying diseases
  - *This target values are either available in the electronic patient file or they are collected at presentation for the study.*
- Relevant previous operations
  - *This target values are either available in the electronic patient file or they are collected at presentation for the study.*
- Current medication
  - *This target value is either available in the electronic patient file or is collected at presentation for the study.*

## 7 Study design

### 7.1 Monocentric / multicentric

This is a monocentric diagnostically cross-sectional study with prospective data acquisition and validation of the data by means of a validation group.

## **7.2 Study arms: intervention/control**

We do not plan interventions. The study will examine two study groups in series. First, the study group 1 will establish thresholds for hemoglobin values using MSOT. Then, in study group 2, the thresholds will be validated and the specificity and sensitivity will be defined.

## **7.3 Randomization**

[figure not shown]
Randomization is not planned.

## **7.4 Blinding**

The examiner is blinded during the measurement and evaluation of the data. The blinding of the examiner occurs because the examiner only performs the measurements but does not know the results of previous tests especially the results of the TASC classification of the previous performed angiography and the results of the CCDS.

Blinding of the patients/test persons is not necessary.

Figure 2 shows the graphic presentation of the study design.

**Figure 2:** Graphical presentation of study design

## 8 Study population

### 8.1 Inclusion and exclusion criteria

#### ***Inclusion criteria:***

- Patients with manifest PAD stages II – IV according to Fontaine or category 1-6 according to Rutherford or healthy volunteer
- Adult (>18 years) persons who are able to give their consent
- Patients with manifest PAD in whom angiography has been performed as part of routine diagnostics (independent of the study) or in accordance with current guidelines, or has been indicated and the patient has given consent; healthy volunteers do not need a previous performed angiography

***Definition of patient groups:***

- PAD IIa with indication for angiography
- PAD IIb with indication for angiography
- PAD III with indication for angiography
- PAD IV with indication for angiography

***Definition of healthy control group:***

- No PAD previously known
- No diabetes mellitus previously known
- No chronic renal insufficiency previously known
- No symptoms in the sense of a Claudicatio intermittens
- ABI with normal value

***Exclusion criteria:***

- Patients with PAD stage I according to Fontaine or category 0 according to Rutherford
- Healthy volunteers with previous known diabetes mellitus or chronic renal insufficiency or abnormal ABI
- Underage persons
- Missing consent form
- Patients with manifest PAD in whom angiography is not indicated
- Exclusion due to safety concerns of the study physician (patient with a physical, mental or psychiatric illness which, in the opinion of the study physician, would compromise the safety of the patient or the quality of the data and thus make the patient an unsuitable candidate for the study)

**8.2 Participant number**

A previous performed valid case number calculation based on the results of the pilot study was not possible due to the small number of patients and cohort studied (PAD IIb, healthy leg versus affected leg).

Based on the data collected until 05.03.2021 the case number calculation (no interim analysis) was performed in cooperation with the Institute of Biometry. Six of a total of 102 persons included up to the above-mentioned date were diagnosed with PAD stage III according to Fontaine. In the course of the study, it became apparent that a sample size calculation based on 30 patients with stage III disease and 30 healthy subjects, as initially planned, could not be realized during a realistic time period.

In order to establish a valid case number as early as possible, the two critical PAD stages III and IV were formally combined into one group to be considered together as chronic critical limb ischemia. Thus, based on the results of a total of 33 healthy study subjects and 29 subjects diagnosed with a critical PAD stage, the exemplary case number calculation could be accomplished. A power analysis, which allowed a power of 80% at an alpha of 0.05 (unilateral) was performed to determine the final sample size. For the MSOT parameter deoxygenated hemoglobin, the number of subjects was approximately 33, and for the MSOT parameter oxygenated hemoglobin, the number of subjects was approximately 11 for each of the individual groups (healthy control group, PAD stage II, PAD stage III-IV).

### **8.3 Recruitment routes and measures**

Patients are informed about the possibility of participating in the study during a routine presentation of the vascular surgery consultation hours in case of previous performed or indicated angiography (existing signed consent form). Healthy volunteers will be acquired via posters in the clinic. If patients or volunteers are willing to participate, they will be fully informed about objectives and methods (especially about the scientific/explorative character of the study), benefits and risks, and the revocability of their participation in the study.

## **9 Study plan**

### **9.1 Procedure for informing about and obtaining consent**

Participants can only be included in the study after a written declaration of consent has been given. The written declaration of consent requires that the participants are informed orally and in written form about the objectives and methods (including the

scientific-explorative character of the study), benefits and risks as well as the revocability of their participation in the study.

It must be clearly communicated to the study participant that a withdrawal of consent is possible at any time and without any disadvantage. Furthermore, all study participants are informed that this study is a purely scientific study without any current diagnostic or therapeutic benefit.

The original of the consent form is kept in the study folder at the study site. The participant receives a copy of the participant information and consent form. The participant information and the consent form for healthy volunteers and patients can be found in the appendix of this study protocol.

## **9.2 Measurements**

After informing the subjects, the determination of underlying diseases, previous performed operations and current medication is performed. If available, this data is determined by the electronic patient file otherwise an anamnesis interview is performed. Underlying diseases, previous operations and medication according to the vascular system is therefore of special interest. The ankle-brachial index is then measured. This parameter is used in vascular medicine to estimate the severity of PAD. For healthy study participants, the measurement of the ABI is considered a screening examination. The participation of healthy subjects in the study requires an inconspicuous value in the ABI measurement (the handling of random findings in the screening process is described in Chapter 13). Prior to this measurement, a resting period of at least 10 minutes in a lying position should be ensured. Then, measurements of the occlusion pressures on both legs and arms are performed. The examination of the ABI lasts a maximum of 20 minutes including the preceding resting period and would also be recorded independently of the study participation during the stationary stay in the context of routine diagnostics in patients with PAD. Afterwards, color-coded duplex sonography of the femoral and popliteal arteries is performed at rest. The CCDS is used to determine the flow profile of the vessels examined and allows an assessment of constrictions or occlusions in these vessels. For this purpose the patient/proband remains lying on the examination couch. Depending on the examination conditions (individual course of the vessels, body size, etc.) this examination takes about 10 minutes. This examination takes place exclusively as part of the study participation and is not part of the routine vascular surgery diagnostics.

The actual current walking distance is used to classify the severity of PAD and will be recorded by a treadmill examination. Under medical supervision, the participants should walk the maximum possible distance on the treadmill at a 12% incline and 3 km/h (standard setting). Should the participant not be able to manage the incline, it will be reduced to 6%. Should that also be impossible, the incline will be reduced to 0%. The walking distance is measured in meters. Since the first 200 meters are of particular importance for the classification of PAD, the study physician terminates the examination when the walking distance exceeds 500 meters. The treadmill examination lasts about 15 minutes and is exclusively part of the study participation; it is not part of the vascular surgical routine diagnostics.

All examinations mentioned above take place in the vascular surgery department. Since the MSOT device is located in the endoscopy rooms of the internal medicine center, the participating persons are transported there by wheelchair after the previously mentioned examinations. It is important that no physical exercise is exerted during transport, as this could falsify the MSOT values. The transport takes about 15 minutes. Afterwards, the examination is performed in the area of the M. triceps surae (in patients in this area of the affected leg) with the MSOT device.

The MSOT examination is performed analogous to a sonography over the corresponding skin layers without further invasive procedures. The anatomical region can be localized by means of built-in B-image sonography; the corresponding optoacoustic signals can then be derived from this. The duration per anatomical region is limited to 5 minutes; participants can remain in a relaxed position during the examination; assistance in the form of breathing maneuvers or similar is not necessary. The position of the transducer is marked with a skin pencil so that the subsequent measurement can be taken over the same region of the muscle. Afterwards, the participant has to complete a defined walking distance of 150 meters, which takes place under medical supervision. This is followed by another measurement of the M. triceps surae using the MSOT. The pilot study showed that active muscle exercises between the two MSOT examinations causes a change in the perfusion parameters and may possibly unmask a stenosis in the lower leg area.

[figure not shown]
If the participant is unable to walk 150 meters between the two MSOT measurements due to previous illnesses or because of the severity of the PAD stage, the walking distance can be reduced in a graduated manner. The first step is to try to cover a

distance of 100 meters. If this is also impossible, the walking distance will be reduced to 50 and finally to 25 meters. In the case of a complete inability to walk, the muscle exposure can alternatively be provoked in a standing position. In this case, the participant should be instructed to change between tip-toe and heel position for at least two minutes. If this form of muscle activity is also impossible, patients can perform extensions and flexions of the foot for at least two minutes while sitting in order to provoke a muscle activity on the lower leg muscles between the two MSOT measurements.

The time required for both MSOT measurements including the muscle activity in between is about 30 minutes. This examination takes place exclusively as part of the study participation and is not part of routine vascular surgery diagnostics.

Independent of the results of this examination, the planned vascular surgery therapy for the patients with PAD (endovascular treatment/vascular surgery, conservative procedure) will be performed according to the guidelines.

Figure 3 shows the graphical presentation of the planned measures as well as their chronological sequence.

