**Figure 3: Graphical presentation of study plan**

### 9.3 Recording of target parameters

- Determination of flow profile of the A. femoralis communis and A. poplitea by CCDS
- Determination of ABI
- Assessment of walking distance by standardized treadmill examination (3km/h with 12% inclination)
- Determination of clinical PAD stage according to Fontaine and Rutherford
- Non-invasive in-vivo measurement by MSOT

- Determination of relevant clinical data: Age, Sex, risk factors for PAD, underlying diseases, previous operations and current medication
  - *These target values are either available in the electronic patient file or they are collected at presentation for the study.*

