- Correlation of acquired MSOT parameters with the ABI [ Time Frame: single time point (1 day)]: Quantitative oxygenated/deoxygenated/total hemoglobin content and MSOTvalues at a wavelength of 800 nm (Units: arbitrary units (a. u.)) derived by transcutaneous MSOT correlated with the ABI
- Correlation of acquired MSOT parameters with the walking distance determined by treadmill examination [ Time Frame: single time point (1 day)]: Quantitative oxygenated/deoxygenated/total hemoglobin content and MSOT-values at a wavelength of 800 nm (Units: arbitrary units (a. u.)) derived by transcutaneous MSOT correlated with the walking distance determined by treadmill examination
- Correlation of acquired MSOT parameters with the clinical severity of PAD [ Time Frame: single time point (1 day)]: Quantitative oxygenated/deoxygenated/total hemoglobin content and MSOT-values at a wavelength of 800 nm (Units: arbitrary units (a. u.)) derived by transcutaneous MSOT correlated with the clinical severity of PAD according to Fontaine and Rutherford

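### Treadmill metres from 12%, 6% and 0% inclines are pooled as one scale, which can attenuate the secondary MSOT–walking-distance correlation by an amount the documents do not let us fix

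*Protocol*

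**What the plan says.** Protocol 9.2 sets the test so that "the participants should walk the maximum possible distance on the treadmill at a 12% incline and 3 km/h (standard setting"). For those who cannot do this, "Should the participant not be able to manage the incline, it will be reduced to 6"%, and then "Should that also be impossible, the incline will be reduced to 0"%. The result is a single number: "The walking distance is measured in meters". There is also an upper limit: "the study physician terminates the examination when the walking distance exceeds 500 meters".

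Protocol 9.3 lists the same variable as "Assessment of walking distance by standardized treadmill examination (3km/h with 12% inclination"), with no mention of the lower inclines. Protocol 6.2 also calls it standardised.

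The SAP makes it a secondary endpoint: "Correlation of acquired MSOT parameters with the walking distance determined by treadmill examination". SAP 9.1 leaves the measure open, naming Pearson and Spearman as examples. SAP 8 summarises continuous variables by mean and SD. Tables 12.3 and 12.4 correlate walking distance with MSOT in patients and in controls. Tables 12.5 to 12.7 show it as mean ± SD by Fontaine, Rutherford, combined TASC and CCDS group, with p-value and ANOVA columns.

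No section makes incline a covariate, stratum or conversion. It is not among the baseline variables (SAP 8.4). The missing-data rule (SAP 7.4) does not cover a stepped-down test or a walk stopped at 500 m.

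**The concern.** Two hundred metres at 12% and 300 m on the flat are results of different tests. On the pooled scale the second person ranks higher, whatever their capacity at a common incline. The easier test goes to people who could not manage the standard one. If that inability partly reflects limited walking capacity, the weakest walkers gain metres and the severity gradient is compressed.

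Ranks inherit the problem, because a change of incline can change the order of participants. The planned group means are affected too: a severe group with many stepped-down tests would show a longer mean distance than it would have had at 12%.

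At stake are one named secondary endpoint and the descriptive walking-distance rows in the sample tables.

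**Working it through.** **Plan's own figure.** There is none for this endpoint. The case numbers in SAP 6 (about 33 and about 11 per group) concern deoxygenated and oxygenated hemoglobin and do not bear on walking distance.

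**Inputs from the documents.** Inclines 12%, 6% and 0%; speed 3 km/h; stop above 500 m; distance in metres; pooled analysis (Protocol 9.2; SAP 4.3, 8, 9.1, 12). About 200 subjects in five similar groups (SAP 5.2), hence about 200 × 4/5 = 160 patients and 200/5 = 40 controls.

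**Assumptions (not in the documents).** Distance at 12% is log-normal, median 150 m (250 m as a variant), log-SD 0.8. Latent correlation with an MSOT readout is 0.5. 20% are tested at 0% and 20% at 6%. Distance is multiplied by m6 at 6% and m0 at 0%.

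**Model.** Recorded distance = min(500, distance at 12% × m), with m = 1 at 12%. True Spearman = (6/π) × arcsin(0.5/2) = 0.48.

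**Step 1: the 500 m stop alone.**
- Median 150 m: ln(500/150)/0.8 = 1.50, so about 6.6% reach the cap. The mean falls from 150 × exp(0.32) = 207 m to 190 m. Spearman goes from 0.482 to 0.481.
- Median 250 m: ln(500/250)/0.8 = 0.87, so about 19% reach the cap. The mean falls from 344 to 278 m. Spearman goes from 0.483 to 0.477.
- Controls have no claudication by definition, so many may reach 500 m. If 95% of 40 do, the Table 12.4 correlation rests on 40 × 0.05 = 2 people below the cap. If all do, it is undefined.

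**Step 2: mixed inclines, pooled metres (median 150 m).**

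| Multipliers (6% / 0%) | Spearman, true 0.48 |
|---|---|
| ×1.3 / ×1.6 | 0.47–0.48 |
| ×1.5 / ×2.5 | about 0.43 |
| ×2 / ×4 | 0.30–0.39 |

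The range in the last row reflects how closely step-down follows walking capacity: about 0.30 if it follows it exactly, 0.33 if it is strongly related to severity with noise, 0.39 if unrelated. Pearson in the noisy case is 0.43 (×1.5/×2.5) and 0.35 (×2/×4). Mean distance in the more severe patients rises from 65 m to 121 m and 175 m respectively.

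The loss is small when few step down. With 5% at each lower incline and ×1.5/×2.5, Spearman is 0.47. If only those below 50 m (6%) and 25 m (0%) step down, the loss is at most about 0.01.

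**Step 3: what the loss means for n.** Fisher z, two-sided 0.05, 80% power: n = ((1.96 + 0.84)/atanh r)² + 3.
- r = 0.48: (2.80/0.523)² + 3, about 32
- r = 0.43: (2.80/0.460)² + 3, about 41
- r = 0.333: (2.80/0.346)² + 3, about 69

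**Step 4: candidate repairs.** Ranking by incline first and metres second, with ×1.5/×2.5:

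| Step-down versus walking capacity | Pooled metres | Incline-first |
|---|---|---|
| follows exactly | 0.44 | 0.48 |
| correlation 0.7 | 0.43 | 0.43 |
| correlation 0.5 | 0.43 | 0.37 |
| unrelated | 0.43 | 0.21 |

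Incline-first ranking is therefore safe only when step-down is almost wholly driven by walking capacity. A rank regression of the MSOT readout on ranked metres plus incline category, read as the joint (multiple) correlation, gave about 0.45–0.49 across these scenarios at the 150 m median. It recovers somewhat less when the median is 250 m, more walks are capped and the multipliers are large.

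**The case against.** The strongest reply is that the size is unsupported. Incline shares, multipliers, typical distances and the expected correlation appear nowhere in the documents, and mild values give almost no loss. That stands, and it rules out saying that the correlation *is* biased toward zero. The documents support only that it can be.

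Second, a reader might infer that the 500 m stop also weakens the correlation. Step 1 does not support this: Spearman, which SAP 9.1 permits, treats capped walks as ties and barely moves. The stop matters for means, SDs and the correlation within controls.

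Third, ranking by incline first looks like the natural cure. It assumes that people step down because of limited walking capacity. The Protocol itself names other reasons: section 10.3 gives dyspnea and orthopedic disorders as grounds for failing the exercise between MSOT measurements, and section 4 cites previous illnesses or operations as reasons why a treadmill test cannot be completed. Anyone stepped down for such a reason would be ranked too low.

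Fourth, the 12% in Protocol 9.3 may be shorthand for the standard setting, and no case report form is shown, so the incline may well be recorded. Both are possible. Neither supplies an analysis rule, and the SAP has none.

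Fifth, the study is described as exploratory and this is one secondary correlation among many. That limits the weight of the point without removing it.

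**Conclusion.** The point holds in a limited form. As written, the plan puts results of non-comparable tests on one scale for a named secondary endpoint, and Protocol 9.2 and 9.3 describe that variable differently. The pooling can attenuate the MSOT–walking-distance correlation and inflate mean distance in severe groups; choosing Spearman does not prevent either. Under the stated assumptions, a true 0.48 is observed as anything from 0.47–0.48 down to 0.30–0.39. Where the study falls in that range cannot be judged without the incline shares and some knowledge of how distance changes with incline.

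A reader might infer that the primary result is at risk, because Protocol 9.2 says walking distance is used to classify severity and SAP 5.4 splits Fontaine IIa from IIb at 200 m. The documents do not support that. The primary endpoint is an MSOT threshold, and SAP 9.3 derives it from controls versus stages III/IV, where the 200 m split plays no part. SAP 5.4 also defines the split by painless distance, and nothing says that stepped-down treadmill metres set the stage.

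**What to change.** None of this changes the test procedure.

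- **Reconcile** Protocol 9.2 and 9.3, so that both describe the same recorded variable.
- **Data set:** enter the final incline for each participant and whether the walk was stopped at 500 m.
- **SAP 9.1, main analysis:** a rank-based analysis with walks stopped at 500 m as ties and incline as a factor (rank regression on metres plus incline category). Report the joint association. The incline-adjusted coefficient for metres alone would discard the part of the association that incline itself carries.
- **Sensitivity:** repeat in 12% tests only, noting that this restricts the range and may itself lower the correlation. Incline-first ranking can be a further sensitivity analysis, but not the main one.
- **Tables 12.3 to 12.7:** for walking distance, report median and IQR, the number at each incline and the number stopped at 500 m, in place of mean and SD. Qualify or drop the walking-distance correlation within controls (Table 12.4) if most are at the ceiling.

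The cost is small: the incline and stop entries, a few lines of SAP text and slightly more analysis on a secondary endpoint. If the incline was not recorded, the tests cannot be separated afterwards, so this should be checked first.
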